7.3. Unscheduled Visits

If, during the investigation, a subject requires an unscheduled visit to the clinical site, the following information will be collected at a minimum:

- Chief complaint prompting the visit. If the reason is an adverse event, the applicable eCRF for the adverse event must be completed and subject record completed as appropriate
- Date and time of the visit and all procedures completed at the unscheduled visit
- Review of adverse event and concomitant medications

Clinical Study Protocol
Johnson & Johnson Vision Care, Inc.

- Documentation of any test article dispensed or collected from the subject, if applicable
- Slit lamp findings (using the Slit Lamp Classification Scale)

If the Investigator withdraws a subject from the study, the final study visit case report forms must be completed indicating the reason(s) why the subject was withdrawn. The subject record must be completed documenting the date and primary reason for withdrawal and the study CRA notified.

Any ocular and non-ocular Adverse Events that are ongoing at the time of the study visit will be followed by the Investigator, within licensure, until they have resolved, returned to pre-treatment status, stabilized, or been satisfactorily explained. If further treatment i.e., beyond licensure is required, the subject will be referred to the appropriate health care provider.

The following information will be collected during an unscheduled visit.

Unscheduled Visit		
Step	Procedure	Details
U.1	Chief Complaints	Record the subject's chief complaints for reasons for the unscheduled visit.
U.2	Adverse Events and Concomitant Medications Review	Review any changes to the subject's medical history or concomitant medications from the previous study visit. Record any changes, and any adverse events.
U.3	Entrance VA	Record the distance Snellen visual acuity (OD, OS, OU) to the nearest letter, and the type of visual correction being worn (study lenses, habitual lenses, distance spectacles or unaided).
U.4	Subjective Sphero-cylindrical Refraction (if applicable)	Perform bare-eye subjective sphero-cylindrical refraction with a phoropter (adopt the maximum plus to maximum visual acuity (MPMVA) approach and use the duo-chrome test for binocular balancing) and record the best corrected distance visual acuity to the nearest letter (OD, OS).
U.5	Slit Lamp Biomicroscopy	FDA Slit Lamp Classification Scale will be used to grade the findings. If the clearance of the fluorescein needs to be expedited, preservative-free rewetting drops may be instilled.
U.6	Exit Visual Acuity	Record the distance Snellen visual acuity (OD, OS, OU) to the nearest letter, and the type of visual correction being worn (study lenses, habitual lenses, distance spectacles or unaided).

Clinical Study Protocol

Johnson & Johnson Vision Care, Inc.

7.4. Laboratory Procedures

None

8. SUBJECTS COMPLETION/WITHDRAWAL

8.1. Completion Criteria

Subjects are considered to have completed the study if they:

- provided informed consent.
- are eligible.
- completed the study visit

8.2. Withdrawal/Discontinuation from the Study

A subject will be withdrawn from the study for any of the following reasons:

- Subject death during the study period.
- Subject withdrawal of consent.
- Subject not compliant to protocol
- Subject no longer meets eligibility criteria (e.g. the subject becomes pregnant).
- Subject develops significant or serious adverse events causing discontinuation of study lens wear.
- Subjects who have experienced a Corneal Infiltrative Event (CIE).
- Investigator's clinical judgment regarding the subject safety reasons (that it is in the best interest of the subject to stop treatment).

For discontinued subjects, the Investigator will:

- Complete the current visit (scheduled or unscheduled).
- Complete the Final Evaluation, indicating the reason that the subject was discontinued from the study.
- Record the spherocylindrical refraction with best corrected distance visual acuity.
- Collect used test article(s) (worn or brought to the visit) from the subject and discard them, unless otherwise stated in section 7.2.
- Make arrangements for subject care, if needed, due to their study participation

An additional subject may be enrolled if a subject discontinues from the study prematurely.

In cases where a subject is lost to follow-up, every possible effort must be made to contact the subject and determine the reason for discontinuation/withdrawal. The measures taken to follow up must be documented including two written attempts and a certified letter (or equivalent) as the final attempt.

Clinical Study Protocol

Johnson & Johnson Vision Care, Inc.

9. PRE-STUDY AND CONCOMITANT INTERVENTION/MEDICATION

Concomitant medications will be documented during screening and updated during the study. Disallowed medications and therapies are medications or therapies that contraindicate contact lens wear. See the Exclusion criteria for specific details.

9.1. Systemic Medications

Certain systemic medications are known to have a higher likelihood to interfere with contact lens wear, chiefly by disrupting the tear film. A summary of disallowed medications is shown in Table 5. Subjects with a history of taking these medications will be allowed to enroll only if:

- The medications have been taken on a continual or routine basis for at least 6 months and the subject has demonstrated successful contact lens wear during this time.

Or

- The subject previously used these medications on a temporary basis and has ceased that medication at least 1 week prior to signing the informed consent.

Table 5: Disallowed systemic medications

Class of Drug	Common Indication(s)	Common Examples
Anticholinergics	Irritable bowel syndrome, Parkinson's disease, peptic ulcer, cystitis, nasal congestion, cold symptoms, overactive bladder, COPD	Bentyl, Spiriva, Atrovent, Hyosyne, Levsin, Symax Fastab, Symax SL, Homax SL, Cogentin, Transderm Scop, etc.
Oral Phenothiazines	Antipsychotic disorders (schizophrenia, mania)	Compazine, Mellaril, Thorazine, Phenergan, etc.
Oral/Inhaled Corticosteroids	Arthritis, colitis, asthma, bronchitis, allergic or inflammatory conditions	Cortisone, Prednisone, Hydrocortisone, Medrol, Kenalog, Flonase etc.
Oral Retinoids	Seborrhea, acne	Isotretinoin, Acitretin, Alitretinoin, etc.
Oral Tetracycline	Urinary Tract Infection, acne, chlamydia, gonorrhea	Sumycin, Achromycin V, etc.

10. DEVIATIONS FROM THE PROTOCOL

Investigator will notify study sponsor upon identification of a protocol deviation. Protocol deviations must be reported to the sponsor within 24 hours after discovery of the protocol deviation. The Investigator will report deviations per IRB/IEC requirements. All deviations will be tracked, and corrective actions implemented as appropriate.

If it becomes necessary for the Investigator to implement a deviation in order to eliminate an immediate hazard to the trial subject, the Investigator may implement the deviation immediately without notification to the sponsor. Within 24 hours after the implemented

Clinical Study Protocol

Johnson & Johnson Vision Care, Inc.

deviation, the Investigator must notify and provide the rationale to the Sponsor and, as required, the IEC/IRB.

If the deviation potentially impacts the safety of patient or changes the technical integrity of the study, then it must be reported to IEC/IRB. This is a "Major Deviation". Deviations that contradict the information contained in the Informed Consent/Assent forms will be considered Major Deviations.

Minor deviations have no substantive effect on patient safety or technical integrity of the study. They are often logistical in nature.

Protocol waivers are prohibited.

11. STUDY TERMINATION

If more than 2 subjects in the investigational soft contact lens group develop serious expected (e.g., definite or probable MK) or unexpected device related adverse events, the study will be suspended. Upon review and consultation with IRB, DMC, and JJVC Safety Management Team, the study may be terminated. This potential stopping rule is established based on our trial involving approximately 200 subjects wearing the investigational soft contact lens for up to 3 years with an assumed MK rate that is below 0.2% per patient-year. The rate of 0.2% per patient year is the established rate for extended wear lenses in adults, which was requested by the FDA as a criterion for evaluating a contact lens for pediatric use in an FDA response to a pre-IDE submission. To be conservative, 200 independent patient years were used in the calculation. The probability of observing 2 cases or more incidents of MK is 0.061, and 3 cases or more incidents of MK is 0.007 (given an MK rate of 0.2% per patient year).

The occurrence of one or more Unanticipated Serious Adverse Device Effect (USADE), or any SAE where the relationship to study agent cannot be ruled out, may result in stopping further dispensing of test article. In the event of a USADE or SAE, the Sponsor may unmask the treatment regimen for the subject(s) and will discuss this with the Investigator before any further subjects are enrolled.

The Sponsor will determine when a study will be stopped. The Principal Investigator always has the discretion to initiate stopping the study based on patient safety or if information indicates the study's results are compromised.

JJVC reserves the right to terminate the study at any time for any reason. Additionally, the IEC/IRB reserves the right to terminate the study if an unreasonable risk is determined. The study can be terminated by the Principal Investigator at the individual clinical site due to specific clinical observations, if in their opinion, after a discussion with JJVC, it is determined that it would be unwise to continue at the clinical site.

Clinical Study Protocol

Johnson & Johnson Vision Care, Inc.

JJVC (and the IEC/IRB and DMC, if applicable) will evaluate all adverse events. If it is determined that an adverse event presents an unreasonable risk, the investigation, or that part of the investigation presenting the risk, will be terminated as soon as possible.

Should the study be terminated (either prematurely or as scheduled), the Investigator will notify the IEC/IRB and Regulatory Authority as required by local regulatory requirements.

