Disallowed Medications/Interventions	
Use of any prescription or over-the-counter (OTC) medications that may affect contact lens wear.
 
See section 9.1 for details regarding disallowed systemic medications.

Measurements and Procedures	
The key measurements are contact lens rotation assessment, requiring the availability of a slit lamp biomicroscope with an adjustable beam orientation and axis dial, or an eyepiece reticle with axis protractor.
 
Subjective questionnaire responses will be recorded by computer-based direct data entry.

Microbiology or Other Laboratory Testing	None

[figure not shown]
Clinical Study Protocol
Johnson & Johnson Vision Care, Inc.

Study Termination	The occurrence of one or more Unanticipated Adverse Device Effect (UADE), or any SAE where relationship to study agent cannot be ruled out, may result in stopping further dispensing investigational product. In the event of a UADE or SAE, the Sponsor Medical Monitor may unmask the treatment regimen of subject(s) and may discuss this with the Principal Investigator before any further subjects are enrolled.
Ancillary Supplies/ Study-Specific Materials	Rewetting drops for optional use during lens wear. Stopwatches will be provided to the site for use during visits.
Principal Investigator(s) and Study Institution(s)/Site(s)	A full list of Principal Investigators, clinical sites, and institutions is kept separately from the Study Protocol and is included in the study Trial Master File.

Clinical Study Protocol

Johnson & Johnson Vision Care, Inc.

Figure 1: Study Flowchart

COMMONLY USED ABBREVIATIONS, ACRONYMS AND DEFINITIONS OF TERMS

ADD	Plus Power Required For Near Use
ADE	Adverse Device Effect
AE	Adverse Event/Adverse Experience
BCVA	Best Corrected Visual Acuity
BSCVA	Best Spectacle Corrected Visual Acuity
CFR	Code of Federal Regulations
CLUE	Contact Lens User Experience
COAS	Complete Ophthalmic Analysis System
COM	Clinical Operations Manager

Clinical Study Protocol

Johnson & Johnson Vision Care, Inc.

COVID-19	Coronavirus Disease 2019
CRA	Clinical Research Associate
CRF	Case Report Form
CRO	Contract Research Organization
CT	Center Thickness
	
D	Diopter
DMC	Data Monitoring Committee
eCRF	Electronic Case Report Form
EDC	Electronic Data Capture
ETDRS	Early Treatment Diabetic Retinopathy Study
FDA	Food and Drug Administration
GCP	Good Clinical Practice
HIPAA	Health Insurance Portability and Accountability Act
IB	Investigator's Brochure
ICF	Informed Consent Form

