3.2. Inclusion Criteria

Potential subjects must satisfy all of the following criteria to be enrolled in the study:

Inclusion Criteria following Screening

The subject must:

1. Read, understand, and sign the STATEMENT OF INFORMED CONSENT and receive a fully executed copy of the form.
2. Appear able and willing to adhere to the instructions set forth in this clinical protocol.
3. Be at least 40 and not more than 70 years of age at the time of screening.
4. Own a wearable pair of spectacles with distance vision correction.
5. Be an adapted soft contact lens wearer in both eyes (i.e. has worn lenses a minimum of 2 days per week for at least 8 hours per wear day, for the past four weeks).

Inclusion Criteria at Baseline Evaluation

The subject must:

6. Have distance spherical equivalent refraction in the range of either -1.00 D to -6.00 D or +1.00 to +6.00 D in each eye.
7. Have distance cylinder refraction in the range of -0.75 to -2.50 D in each eye, with the axis being in the range of either $90 \pm 30^\circ$ or $180 \pm 30^\circ$.
8. Have best corrected distance visual acuity of 20/25 or better in each eye.

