4. STUDY DESIGN AND RATIONALE

4.1. Description of Study Design

The study is a bilateral, single-masked, single-visit, non-dispensing 2x2 crossover study. Up to 90 (45 Hyperopes and 45 Myopes) subjects will be enrolled with the aim of 80 subjects (40 Hyperopes and 40 Myopes) to complete the study.

Eligible subjects will be randomized to receive two investigational multifocal toric lenses in a random order at the single study visit. Subjects will be fitted, and evaluations of toric and mechanical lens fit will be conducted as well as assessment of subjects' initial comfort and handling. Each lens will be worn for approximately forty (40) minutes. Lens powers fit on subjects during this study are unlikely to be an exact match to their refractive error (ie., They may under-correct or over-correct the sphere and/or cylinder) and will therefore provide sub-optimal vision correction during the brief wearing period while rotation and comfort are evaluated.

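### Section 11 takes its suspension threshold (more than 2 subjects) from a 200 patient-year trial; this single-visit study has about 0.014 to 0.25 patient-years

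*Combined protocol and SAP*

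**What the plan says.** **The rule.** Section 11 (Study Termination) begins "If more than 2 subjects in the investigational soft contact lens group develop serious expected", gives definite or probable MK as an example, adds unexpected device-related events, and requires suspension. Termination may follow after consultation with the IRB, a DMC and the sponsor's Safety Management Team.

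**Its stated basis.** The rule is attributed to "our trial involving approximately 200 subjects wearing the investigational soft contact lens for up to 3 years", with an assumed MK rate below 0.2% per patient-year. Section 11 describes 0.2% as the established adult extended-wear rate, which the FDA requested as "a criterion for evaluating a contact lens for pediatric use". It adds: "To be conservative, 200 independent patient years were used in the calculation". The probabilities printed are 0.061 for two or more cases and 0.007 for three or more.

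**This trial.** Section 3.2: "Be at least 40 and not more than 70 years of age at the time of screening". Section 4.1: up to 90 enrolled, two lens types per subject, and "Each lens will be worn for approximately forty (40) minutes". Section 4.3: one visit per subject. Section 16.4: a DMC is not applicable.

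**After a single event.** Both texts say that further dispensing may be stopped after one unanticipated device effect or one possibly related SAE. On what happens before more subjects are enrolled they differ. The synopsis (Study Termination) says the Medical Monitor "may discuss this with the Principal Investigator before any further subjects are enrolled". Section 11 says the Sponsor "will discuss this with the Investigator before any further subjects are enrolled".

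**The concern.** A count threshold balances false alarms against delay in reacting to a real signal. That balance depends on the exposure in the trial where the rule is used. In a long trial some background MK is expected, so waiting for a third case avoids suspending on chance. In a study lasting a few hours per subject almost none is expected, and a first case is already a strong signal.

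The only numerical trigger in this protocol has false-alarm properties that belong to another design. By the time it operates, 3 of 90 subjects (3.3%) would be affected. After a first or second event, a pause depends on judgement, or on a discussion clause that is mandatory in Section 11 and optional in the synopsis. The consultation step also names a committee this study does not have.

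**Working it through.** **Step 1. Reproduce Section 11's figures.** Inputs: 200 patient-years and 0.002 per patient-year (Section 11).

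- Binomial, 200 independent patient-years at 0.002: P(≥2) = 0.0614 and P(≥3) = 0.0078.
- Poisson, mean 200 × 0.002 = 0.4: P(≥2) = 0.0616 and P(≥3) = 0.0079.

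The printed 0.061 is reproduced. The printed 0.007 is 0.0078 truncated. If the source trial ran its full 200 × 3 = 600 patient-years (mean 1.2), the values would be 0.337 and 0.120, so the printed figures do rest on 200.

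In that trial P(≥1) = 1 − exp(−0.4) = 0.330. One background case had a one-in-three chance, which is why a threshold of one would have been unsuitable there.

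**Step 2. Exposure in this trial.** Inputs: 90 subjects, two lens types, 40 minutes each (Section 4.1).

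- Lens wear only: 90 × 2 × 40 min = 7,200 min = 120 h; 120 / (24 × 365.25) = 0.0137 patient-years.
- One day at risk per subject (assumed): 90 / 365.25 = 0.246 patient-years.

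The documents do not say how time at risk should be counted after 80 minutes of wear, so windows of 7 and 14 days are shown as assumptions too.

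**Step 3. Chance of one background MK case here.** P(≥1) = 1 − exp(−0.002 × patient-years).

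| Time at risk per subject | Patient-years | 200 ÷ patient-years | P(≥1 MK) |
|---|---|---|---|
| Wear time only (80 min) | 0.0137 | about 14,600 | 0.003% |
| 1 day (assumed) | 0.246 | about 810 | 0.05% |
| 7 days (assumed) | 1.72 | about 116 | 0.34% |
| 14 days (assumed) | 3.45 | about 58 | 0.69% |

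P(≥3) is about 3.4 × 10⁻¹⁵ on wear time and 2.0 × 10⁻¹¹ on one day, against the printed 0.007.

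**Step 4. Break-even.** A first-case trigger here has the 0.7% false-alarm chance that Section 11 accepts for three cases when exposure is −ln(1 − 0.007) / 0.002 = 3.51 patient-years. That is 3.51 × 365.25 / 90 = 14.3 days per subject. For any shorter window, suspending on the first MK case gives fewer false alarms than the borrowed rule was meant to allow.

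**Step 5. What the rule covers.** MK is only an example in Section 11. Section 13.1 lists other ocular SAEs, including iritis, uveitis, central corneal opacity and persistent epithelial defect. No rate is given for these or for unexpected device-related events, so the probabilities above apply to MK alone.

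**The case against.** The strongest reply is that the count rule is one safeguard among several and would almost never operate.

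- Serious and significant events must reach the sponsor within 24 hours (Sections 13.4 and 13.4.1).
- A UADE must be evaluated and reported to the FDA, the IEC/IRB and the investigators within 10 working days (13.4.1).
- Section 11 requires prompt termination if an event is judged to pose an unreasonable risk, and the sponsor, IEC/IRB and investigator keep discretionary powers.
- Section 11, unlike the synopsis, already requires discussion before further enrolment.

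All of this stands. A reader might infer that subjects are unprotected until a third event; the documents do not support that. What remains is that the one numerical trigger has no valid basis here.

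Three other inferences also go too far:

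- *A pediatric rate was applied to adults.* Section 11 calls 0.2% an established adult rate; only its use as a regulatory criterion was pediatric. The mismatch lies in trial size and duration.
- *Exposure is simply 14,600 times smaller.* That counts lens-on-eye minutes, and the documents do not say the 200 patient-years were counted that way. One day per subject gives about 810. The conclusion is the same.
- *The rule could be replaced by first-event suspension for MK or a UADE alone.* Under 13.1 a UADE must not have been previously identified in the plan, brochure or protocol. Device-related iritis or uveitis, being listed, might not qualify. Three such cases force suspension today, so the narrower replacement would weaken protection.

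**Conclusion.** The point holds, as a minor one. The threshold and its probabilities describe a 200 patient-year trial, not this one. At the rule's own 0.2% rate, a single background MK case has a chance of about 0.003% (wear time) to 0.05% (one day per subject), rising to about 0.7% with a 14-day window. The case for tolerating two therefore falls away. This rests on 90 enrolled subjects, about 40 minutes per lens type, and assumed risk windows of up to 14 days; it is a statement about MK only.

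The disagreement between synopsis and Section 11 on discussion, and between Section 11 and 16.4 on a DMC, are plain inconsistencies in current text. Nothing here shows that subjects would be harmed, and the primary analysis of rotation is not affected.

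**What to change.** 1. In Section 11, delete the 200-subject, 3-year rationale and its probabilities.
2. State that enrolment and lens insertion are suspended on the first serious device-related event: any SAE listed in 13.1, including definite or probable MK, judged related or possibly related, or any UADE. Suspension lasts until the medical monitor, with the Safety Management Team and the IRB as required, documents a restart decision.
3. State that qualifying events reported after the visit count. Section 13.3 leaves recording of after-exit events to the Investigator's discretion, and with a visit of about 2.5 hours (Table 4) an event that takes longer to appear will be reported after exit.
4. If the sponsor wants automatic first-event suspension only for MK or a UADE, keep the existing rule of more than 2 subjects as a backstop for everything else it now covers.
5. Remove the DMC from the consultation sentence, to agree with 16.4.
6. Make the synopsis match Section 11, so that discussion before further enrolment is mandatory in both.

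The other stopping, notification and evaluation provisions stay as they are.

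**Cost.** Wording only, with no added subjects, visits or committee. If triggered, there is a short enrolment pause. The chance that background MK alone causes one is the range in the table above. Rates for other qualifying events are not given, but Section 1.5 reports no serious event in three prior studies of similar lenses, covering about 37 + 32 + 86 = 155 wearers (37 is the number completing the first study; 32 and 86 are numbers dispensed).
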